remain positive years after treatment has cleared microfilaremia. The antigen tests will be performed in individual residents over 5 years of age. This will be done by sampling approximately 100 randomly selected households per sentinel site (village) to produce N of 400. There will be 4 sentinel sites for each treatment zone (annual vs twice annual MDA). The target number of samples per village is close to the minimum sample size of 335 needed to show that the rate of antigenemia (card test) positivity is less than 2% (with 95% confidence and 80% power). In post-MDA populations, this corresponds to a MF rate of less than 0.5%, which is an LF elimination target. We expect to collect 4 to 5 blood samples per household. Subjects with positive card tests will be tested for microfilaremia with 60 µl night blood thick smears. Our decision to detect MF by thick smears of finger prick blood rather than membrane filtration of venous blood is because thick smears are recommended for LF elimination program guidelines. In addition, our prior studies in Egypt have shown that L3 production by *Culex* mosquitoes that feed on MF carriers with negative thick smears is negligible. The justification for collecting blood at night for MF testing is that microfilariae of *W. bancrofti* and *B. timori* in Indonesia are nocturnally periodic with highest counts in peripheral blood between 9 p.m. and 2 a.m.

Blood tests for *Brugia timori* infection *B. timori* infections will be detected by two methods, namely microscopic examination and the BrugiaRapid Test (BmR1 antibody) Cassette (Cellabs, Malaysia). Microscopic examination of thick blood smears prepared with 60 µl of blood collected between the hours of 9 p.m. and 2 a.m. The Brugia Rapid test is a rapid diagnostic test kit for detecting antibodies to filarial parasites using serum or whole blood.

Blood samples will be collected from randomly selected households per sentinel site (village) to produce N of 400. There will be 4 sentinel sites for each treatment zone (annual vs twice annual MDA). This sample size number exceeds the minimum target sample size of 335 needed to show that the MF rate is less than 2% (with 95% confidence and 80% power, assuming an actual rate of 0.5%, which is an LF elimination target). We expect to collect 4 to 5 samples per household.

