7.2 Sample Size Considerations

Except as otherwise noted, all sample sizes in this protocol were calculated using a binomial power calculator (using alpha = .05, two-tailed tests, and power = .80). These sample sizes were chosen to provide confidence that measured prevalence rates will be below specified limits based on assumptions regarding true prevalence rates. The sample size analysis considered various contingencies to assess robustness of the sample size estimates (see Appendix).

Note: Sample size considerations for community surveys for demonstrating that prevalence rates are below pre-defined targets for antigenemia, microfilaremia, antifilarial antibody and STH infections are provided in Section 4, above, and this is not repeated here.

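### The 335-per-village minimum for showing a B. timori MF rate below 2% does not reach its stated 80% power (76.4% one-sided, exact); the one-sided minimum is 386, which the planned 400 exceeds

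*Combined protocol and SAP*

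**What the plan says.** Section 4 (Study Design), in the paragraph on blood tests for *B. timori*, plans 400 persons per sentinel village and adds: "This sample size number exceeds the minimum target sample size of 335 needed to show that the MF rate is less than 2" per cent. The conditions follow directly: "with 95% confidence and 80% power, assuming an actual rate of 0.5%, which is an LF elimination target".

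The *W. bancrofti* antigen paragraph of Section 4 uses the same number: "The target number of samples per village is close to the minimum sample size of 335 needed to show that the rate of antigenemia" positivity is below 2%, again with 95% confidence and 80% power. It gives no assumed true antigen rate for that calculation.

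Section 7.2 gives the purpose of the sample sizes: "chosen to provide confidence that measured prevalence rates will be below specified limits based on assumptions regarding true prevalence rates". It gives the method as "calculated using a binomial power calculator (using alpha = .05, two-tailed tests, and power = .80", except where otherwise noted. For the community surveys it refers back to Section 4. It also refers to an Appendix on contingencies, which is not in the supplied text.

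On sampling, Section 4 says: "We expect to collect 4 to 5 samples per household". Neither section gives a village size or an intra-household correlation.

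**The concern.** The stated aim fixes where each error rate belongs. To show that a rate is below 2% with 95% confidence, the 5% error must apply at a true rate of 2%: it is the chance of wrongly declaring the village below the limit. The 80% power must apply at the assumed true rate of 0.5%. With the errors placed that way, 335 does not come out as the minimum.

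Section 7.2 sends the reader to Section 4 for the survey sizing, so 335 is the visible reason for 400 per village. If 335 is wrong, the claim that 400 exceeds the minimum needs its own check. What is at stake is the accuracy of that justification, not the comparison of annual with twice-yearly MDA.

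**Working it through.** **Inputs.** Limit 2%, true rate 0.5%, 95% confidence, 80% power, stated minimum 335 and planned 400 (Section 4). Alpha 0.05, two-tailed, binomial calculator (Section 7.2). Assumed here: independent persons and, in steps 1 to 3, a large village.

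**Method.** Let X be the number of positives among n. Take H0: p ≥ 0.02 and the alternative p = 0.005. The cut-off c is the largest integer with P(X ≤ c | n, 0.02) ≤ α. Power is P(X ≤ c | n, 0.005). Use α = 0.05 for a one-sided test and 0.025 for the lower tail of a two-tailed test.

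**Step 1: try to reproduce 335 as stated.** At n = 335 and p = 0.02, P(X ≤ 1) = 0.0090, P(X ≤ 2) = 0.0358 and P(X ≤ 3) = 0.0965.
- One-sided: c = 2. Power = 0.1865 + 0.3140 + 0.2635 = 0.7640.
- Two-tailed: c = 1. Power = 0.1865 + 0.3140 = 0.5005.

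Neither is 80%. One-sided, no n below 386 reaches 80%; the best is 79.3%, at n = 313.

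**Step 2: the exact minimum, and the planned 400.**

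| n | Test | Cut-off | Error at 2% | Power at 0.5% |
|---|---|---|---|---|
| 335 | one-sided | ≤2 | 0.0358 | 76.4% |
| 386 | one-sided | ≤3 | 0.0495 | 87.0% |
| 400 | one-sided | ≤3 | 0.0410 | 85.8% |
| 335 | two-tailed | ≤1 | 0.0090 | 50.1% |
| 400 | two-tailed | ≤2 | 0.0131 | 67.7% |
| 436 | two-tailed | ≤3 | 0.0248 | 82.4% |

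One-sided, 386 is the minimum and every larger n also meets 80%. Two-tailed, 80% is first reached at 436. Power then falls below 80% again for n = 460 to 508 and holds for every n only from 509.

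**Step 3: where 335 does appear.** Exchange the roles: null 0.5%, alternative 2%, reject at X ≥ 5.
- n = 335: alpha = P(X ≥ 5 | 0.005) = 0.0277; power = P(X ≥ 5 | 0.02) = 0.8007.
- n = 334: power = 0.7986.

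So 335 is exactly the minimum for the exchanged problem, either one-sided at 0.05 or with a two-tailed minimum-likelihood p-value. At 0.025 per tail the exchanged minimum would be 394. Equivalently, in the stated direction, 335 is the first n for 80% confidence and 95% power: with ≤4 positives the error at 2% is 0.1993 and the power at 0.5% is 0.9723.

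**Step 4: finite villages.** Village size is not given, so the sizes below are assumptions. The calculation is hypergeometric, with 2% and 0.5% of the eligible persons positive.

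| Assumed eligible persons | 335, one-sided | 335, two-tailed | 400, two-tailed |
|---|---|---|---|
| 1,000 | 78.8% | 78.8% | 91.4% |
| 1,200 | 78.2% | 78.2% | 90.0% |
| 1,400 | 77.9% | 77.9% | 89.2% |
| 1,600 | 77.6% | 77.6% | 88.7% |
| 2,000 | 77.3% | 48.1% | 67.8% |
| 10,000 | 76.6% | 49.7% | 67.7% |

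At an assumed 600 to 800 persons, one-sided power at 335 is above 80%.

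**The case against.** **400 is planned, so 335 does not matter.** This largely stands on a one-sided reading. Section 4 states a one-directional criterion, and Section 7.2 applies its two-tailed rule only where nothing else is noted. On that reading 400 exceeds the correct minimum of 386. Only the printed minimum and its power are wrong.

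**The two-tailed figures depend on village size.** This stands. The 50.1% and 67.7% need villages of about 2,000 or more eligible persons. In villages of 1,000 to 1,600, 400 gives about 89–91% even two-tailed. They should not be quoted without that condition.

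**The calculator's algorithm is not stated.** This stands in part. The arcsine formula needs 306 one-sided and 388 two-tailed; the normal approximation needs 373 and 496. The correct minimum therefore varies with the method, but none of these gives 335 in the stated direction.

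**The swap is not documented.** This stands. The match is exact, but the null is not stated and the Appendix is not available, so the swap is an inference.

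A reader might also infer more than the documents support:
- *Villages truly at 2% would be passed in about 20% of surveys.* That 19.9% belongs to a rule of ≤4 positives in 335. No section sets a village pass rule.
- *The regimen comparison is underpowered.* Section 7.4 tests it with a generalized linear mixed model that does not use 335 and already allows for household clustering.
- *More people must be enrolled.* On the one-sided reading 400 is enough before clustering. Otherwise the answer turns on sidedness and village size, which the plan leaves open.

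**Conclusion.** The point holds, as a minor one. For the aim stated in Section 4, 335 gives 76.4% power one-sided, 3.6 points below the stated 80%, and the exact minimum is 386, 51 more than printed. The planned 400 exceeds that minimum with 85.8% power. If the two-tailed alpha of Section 7.2 governs and villages are large, the claim that 400 exceeds the minimum fails (67.7% power; 80% held throughout only from 509).

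These figures rest on an exact binomial test, independent persons and, except in the finite-population table, a large village. Positive correlation within households of 4 to 5 sampled persons would lower them; without an intra-household correlation in the plan, the size of that loss is not estimated here. An exchange of the 5% and 20% error rates is the likeliest origin of 335, but remains unconfirmed.

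**What to change.** 1. In Sections 4 and 7.2, state the null rate, the alternative rate and the sidedness of the village-limit calculation.
2. If one-sided: replace 335 by 386 and give the power at 400 as about 86%.
3. If two-tailed is kept: give the power at 400 as about 68%, or state the village size and give a finite-population figure. Remove the statement that 400 exceeds the minimum, and quote 509 as the minimum (first crossing 436).
4. Say that these figures are before household clustering, which would lower them.
5. In the antigen paragraph, correct or justify the same 335 and give the assumed true antigen rate.

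The cost is text changes in two sections, with no added enrolment and no change to the planned analysis. The sponsor has to commit to one sidedness, and the printed justification becomes somewhat less favourable.

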5 STUDY POPULATIONS

Description of human subject involvement in research:

We will perform repeated annual cross-sectional surveys in study communities.

Eligibility: This project will study people who live in communities that are endemic (or that were endemic at the beginning of the study) for LF. The endemicity rate (MF rate) at baseline should be at least 10% and study areas should have limited or no prior experience with MDA for LF.

Gender, minority and child inclusion: Males and females will be included in population-based village studies without regard to race, religion, or ethnic group. There is no reason to exclude pregnant women and older children from population-based studies. Exclusion of children less than 6 years of age from community studies is justified because prevalence rates for filariasis tend to be very low in young children and because of difficulties associated with collecting clinical specimens from this population.

6 STUDY PROCEDURES / LABORATORY EVALUATIONS

Study procedures include collection of blood and testing for microfilaremia, filarial antigenemia and anti-filarial antibodies. We will perform stool examination to detect STH infections.

All assays will be performed in Indonesia (filarial antigen and antibody tests, MF smears, stool examinations). Some samples will be tested in parallel at Washington University for QC.

6.1 Laboratory Evaluations

The **rationale** for performing these tests is described in some detail in Section 4 (study design) above. Briefly, the study calls for collection of blood that will be tested for microfilaremia (60 µl thick blood smear) and filarial antigenemia (75-100 µl blood, Binax Now Filariasis Card Test and/or Alere Filariasis Strip Test) and anti-filarial antibodies ((25-35 µl), BrugiaRapid (BmR1) cassette test-**Sikka district only**) and for collection stool (at least 1g of stool) that will be tested for the presence of STH infections.

Test methods:

Filarial antigen testing: The Binax Now Filariasis Card Test and/or Alere Filariasis Strip Test (Alere, Portland, Maine) will be performed according to manufacturer's instructions. Briefly, the subject's finger is cleaned with an alcohol wipe, dried with sterile cotton, and stuck with a sterile lancet. Finger blood is collected with a 75-100 µl capillary tube and placed on a sample pad on the

one or both filariasis tests. The result is read at 10 minutes. If desired, test results can be fixed by adding a drop of ethanol or methanol to the nitrocellulose strip of either tests..

Anti-Filarial antibody testing: In addition to rapid antigen tests, Brugia Rapid (BmR1) antibody test (Cellabs, Malaysia) will be performed according to manufacturer's instructions but only in the Sikka district where *W. Bancrofti* and *Brugia infections* are co-endemic. Blood will be collected by finger prick into EDTA anticoagulated microcontainer tubes. Sera may be separated by centrifuge. Sera (25 µl) will be tested on the BrugiaRapid Test (BmR1). Results are provided within 15 minutes for sera and 20 minutes for whole blood.

Microfilaria (MF) detection: For both filarial infections three-line thick smears are prepared with a measured total 60 µl of finger prick blood collected between 9 pm and 2 am. Slides are fixed, stained with Giemsa, and examined by microscopy with a 10x objective (higher magnification for suspicious objects). The species of MF will be determined by morphological criteria.

Testing stool for ova of soil transmitted helminths. Stool will be collected in 25 ml containers and preserved in formalin (final concentration 5%). One gram of stool will be examined using the FLOTAC method [10]. This method provides a sensitive means of detecting and quantifying helminth eggs. Some stools will also be tested with traditional parasitological methods currently used in Indonesia for comparison with FLOTAC results. In Indonesia *Ascaris lumbricoides*, hookworms and *Trichuris trichiura* are the mosty prevalent STH. Eggs/larvae of other STH will be recorded, but not statistically analyzed.

6.2 Instructions for Specimen Preparation, Handling, and Storage

Finger prick blood will be collected in Eppendorf or microtainer tubes with EDTA anticoagulant and diagnostic tests will be performed within 48h following collection. rapid LF antigen tests (Binax Now Filariasis Card Test or Alere Filariasis Strip Test) will be read in day light 10 minutes after finishing the procedure as required for the current test. BmR1 will be tested any time after blood collection. All persons will be tested for blood microfilaremia by thick smear examination (60 µl). Blood samples will be stored at RT or 4°C (if available) and away from direct sunlight.

Stool samples will be preserved with formalin (final concentration 5%) and stored at room temperature for later examination for helminth eggs. Samples will be labeled with barcode numbers that can be linked to unique identifiers (ID numbers).

Safety: Project personnel will treat all human blood and stool specimens as if they were infectious, and we will comply with OSHA safety regulations (29CFR part 1910,1030). **Field personnel will wear gloves, and laboratory personnel will wear gloves and lab coats for protection while working with blood or stool samples.**

6.3 Specimen Shipment

All samples will be tested in Indonesia. Some preserved stool samples and questionable blood smears will be tested in parallel in the reference laboratory at Washington University in St. Louis for quality control. This will be performed together with UI scientists. Shipment will comply with University of Indonesia rules and with IATA regulations.

7 STATISTICAL CONSIDERATIONS

7.1 Study Outcome Measures

The following variables will be treated as binary variables: Microfilaremia, antigenemia, anti-filarial antibody, stool parasites (*Ascaris*, Hookworm, and *Trichuris*). Microfilaria counts will also be recorded (MF/60 µl smear), and stool egg counts per species will be recorded as eggs/gram of feces.

7.2 Sample Size Considerations

Except as otherwise noted, all sample sizes in this protocol were calculated using a binomial power calculator (using alpha = .05, two-tailed tests, and power = .80). These sample sizes were chosen to provide confidence that measured prevalence rates will be below specified limits based on assumptions regarding true prevalence rates. The sample size analysis considered various contingencies to assess robustness of the sample size estimates (see Appendix).

Note: Sample size considerations for community surveys for demonstrating that prevalence rates are below pre-defined targets for antigenemia, microfilaremia, antifilarial antibody and STH infections are provided in Section 4, above, and this is not repeated here.

7.3 Participant Enrollment and Follow-Up

This project aims to enroll approximately 6,400 subjects per year for two study areas (total for *W. bancrofti* and *B. timori* sub-projects). Each of the two study areas (one for *Brugia and Wuchereria (Sikka)* and one for *Wuchereria (Java)*) will have cluster surveys of approximately 400 people per village for 4 villages from annual MDA areas and 400 people per village for 4 villages from twice per year MDA areas.

The community/household surveys are cross-sectional with no follow-up planned.

7.4 Statistical Analysis Plan

The following outcome variables will be collected and treated as binary variables: Microfilaremia, antigenemia with the Binax Now Filariasis Card Test and/or the Alere Filariasis Strip Test, anti-filarial antibody (*Brugia* endemic area only) and stool parasites (separate analysis for *Ascaris*, *Trichuris*, and Hookworm). Microfilaria counts (recorded as

MF/60 µl smear) and stool egg counts per species (recorded as eggs/gram of feces) will be taken as count variables.

Data will also be collected for demographic characteristics and covariates including age, gender, history of lymphedema, scrotal swelling (hydrocele), and prior treatment for LF.

For demographic characteristics variables, descriptive statistics will be examined for the individuals who participate in the trials by sentinel site (village) and over years of observation. Frequency will be tabulated for categorical variables. Descriptive statistics (mean, median, range and standard deviation) will be obtained for continuous variables.

Impact of MDA on study outcome measures

1. Testing primary hypothesis

The primary hypothesis is that twice annual MDA is superior to annual MDA for eliminating LF. The binary outcome variables used to test this hypothesis include microfilaremia and antigenemia and anti-filarial antibody (*Brugia* endemic area only). The model which is being used will fit a linear trend over time within each village. The mean slope across villages within each treatment group will then allow estimates of time to target levels for control (microfilaremia < .5% and antigenemia < 2%) for a selection of baseline prevalences. To illustrate the analysis strategy, we use antigenemia as an example.

The antigenemia prevalence is expressed as filarial antigenemia rate (proportion of examined individuals with filarial parasite antigenemia detected with the Binax Now Filariasis Card Test). To estimate the effect of MDA on antigenemia prevalence, we will tabulate mean rates of antigenemia across the four sentinel sites from each treatment zone (annual vs. twice annual MDA) over years of observation including the baseline. A generalized linear mixed model (GLMM) **with a logistic link function** will be used to account for the correlation of observations clustered within the same household from the same sentinel site. The model to estimate the difference in the odds of antigenemia includes treatment regimen and year of observation, and interaction between treatment regimen and year of observation. Some covariates that will be adjusted for in the analysis include sentinel sites, history of lymphedema, scrotal swelling (hydrocele) and prior treatment for LF as well as demographic variables of interest. Modeling will be performed with use of PROC GLIMMIX in SAS 9.2. CONTRAST statements will be used to test the significance of the log odds of antigenemia between the two treatment regimens at each year of observation. The difference of slope of rate decrease between the two regimens over the years of observations will also be tested with CONTRAST statements in PROC GLIMMIX. The resulting estimates will be converted to odds ratios with 95% confidence interval calculated from the robust estimator of variance. The other binary outcome variables (microfilaremia and anti-filarial antibody) will be analyzed with the same technique.

With microfilaria (per 60 μ l of blood) measured as counts, we will display mean counts of microfilaria across the four sentinel sites from each treatment zone (annual vs. twice annual MDA) over years of observation including the baseline. To accommodate zero counts in modeling, we will use Geometric mean intensity (GMI) of circulating microfilaria. GMI is calculated as $\text{antilog}[(\sum \log(x+1))/n] - 1$, where x is the number of microfilaria per 60 mm^3 of blood and n is number of subjects. A generalized linear mixed model (GLMM) (implemented in PROC GLIMMIX) will be used to account for correlation of observations resulted from clustering. CONTRAST statements will be used to test the significance of differences in GMI of antigenemia between the two treatment regimens at each year of observation. The resulting estimates of GMI will be presented with 95% confidence interval. All statistical tests will be two-sided at a significance level of 0.05, but one-sided p-value will be reported according to the hypothesis. Similar analytic models will be done for community Mf loads and community egg load for each of three intestinal worm eggs.

The cost analysis comparing the two treatment regimens will be conducted by [name] of the George Washington University School of Public Health and Health Services. The model will also allow cost effectiveness analysis when combined with the efficacy analysis.

2. Testing secondary hypothesis

The secondary hypothesis is that twice annual MDA is superior to annual MDA in controlling STH. The primary endpoint for assessing the impact of MDA on STH infections is community egg load (average stool egg count per species). The analysis strategy for these end points is the same for microfilaria count in testing the primary hypothesis.

Adverse event

Since this is a minimal risk and nonintervention study, adverse events are not expected to be an issue. However, subjects will be monitored for adverse events related to blood collection. Proportion of subjects with an adverse event will be tabulated with 95% confidence interval for each sentinel site at each year of observation.

Treatment coverage rate

Treatment coverage rate of the eligible population will be reported from the repeated cross-sectional surveys for the sentinel sites (villages) during different rounds of treatment. Differences in treatment coverage rates will be evaluated between the two treatment regimens (annual vs. twice annual MDA) over time with the use of Chi-square test.

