4 STUDY DESIGN

(Please read this section together with Section 5, “Study Population”)

The project is comprised of repeated annual cross-sectional surveys in sentinel communities before and after initiation of MDA for LF. MDA (standard regimens recommended by WHO) will be provided by government health officials. Data collection will include demographic data, history of lymphedema, scrotal swelling (hydrocele), acute filarial fever or adenolymphangitis, prior treatment for LF. Blood samples (400 µL per person) will be collected from systematically sampled households. Blood will be tested for filarial antigenemia with the Binax Now Filariasis Card Test and Alere Filariasis Strip Test (which detects *Wuchereria bancrofti* antigen in blood, manufactured by Alere, Portland ME, USA). Blood from persons with positive filarial antigen tests will also be tested for microfilaremia (see Section 6 below for methods). The *Brugia* Rapid (BmR1) test will be used to detect antibodies to *Brugia* parasites antibodies in serum or blood samples. Stool examinations will also be performed for diagnosis of STH infections. **Note not all test will be performed on blood and stool samples.**

Safety oversight: Study personnel will monitor subjects for adverse events related to blood collection. No medical monitor or DSMB is needed for this minimal risk, non-intervention study.

Time to collect specimens: Most participants in the community will only be studied once (demographic data, blood, and stool samples). Thus, the **duration** of subject participation will be one day.

Parameters and criteria for assessing the impact of MDA:

Blood tests for *Wuchereria bancrofti* infection, Binax Now Filariasis Card Test and Alere Filariasis Strip Test (with MF testing of antigen positive subjects): We are using these tests as a measure of LF endemicity. The rapid tests detect antigen released from living adult filarial worms potentially capable of resuming MF production in the future. The antigen tests are much more sensitive for *W. bancrofti* infection than tests for microfilaremia. However, antigen tests may

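### The primary comparison of twice-yearly with annual MDA has no stated between-village error term, although regimen varies only between villages (4 v 4 per area)

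*Combined protocol and SAP*

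**What the plan says.** Section 4 sets the layout: "There will be 4 sentinel sites for each treatment zone (annual vs twice annual MDA"), and MDA "will be provided by government health officials". Section 7.3 repeats it for each study area: "cluster surveys of approximately 400 people per village for 4 villages from annual MDA areas" and the same number from twice-yearly areas.

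Section 7.4, under the primary hypothesis, describes the analysis twice.

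- The opening paragraph says: "The model which is being used will fit a linear trend over time within each village". It continues: "The mean slope across villages within each treatment group will then allow estimates of time to target levels for control".
- The worked example for antigenemia, whose technique is then applied to the other binary outcomes, specifies a logistic GLMM that "will be used to account for the correlation of observations clustered within the same household from the same sentinel site". Its effects are regimen, year and their interaction. On adjustment it says: "Some covariates that will be adjusted for in the analysis include sentinel sites, history of lymphedema, scrotal swelling (hydrocele) and prior treatment for LF". CONTRAST statements test the regimens against each other at each year and test the difference in slope. Odds ratios come with a "95% confidence interval calculated from the robust estimator of variance".

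The worked example names no village random intercept, village random slope or village-by-year term. It gives no denominator degrees of freedom and does not say at what level the robust variance is clustered.

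**The concern.** About 1,600 people per regimen are examined in each area each year (4 × 400), but they come from only four villages per regimen. Villages can differ in how fast infection falls for reasons unrelated to regimen, such as coverage, vector density or migration. A test of the regimen effect has to ask whether the two sets of four villages differ by more than villages ordinarily differ from one another. A model that recognises only household correlation asks a different question and treats thousands of people as the replication.

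This is the test of the primary superiority hypothesis, and its efficacy result feeds the cost-effectiveness analysis. If the error term is too small, the intervals are too narrow. Twice-yearly MDA, with the extra resources it needs, could then be declared superior because of ordinary village-to-village variation.

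**Working it through.** **Layout.** Two areas × (4 + 4) villages × 400 people = 6,400, which reproduces the yearly enrolment in section 7.3. The sample sizes explained in section 4 concern showing that prevalence is below a limit; they are not for the comparison of regimens.

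**What can be estimated.** Take eight village indicators, regimen, five surveys as categories (four indicators) and regimen by year (four): 8 + 1 + 4 + 4 = 17 columns. The rank is 16, and it stays 16 when the regimen column is dropped. With villages as fixed covariates, regimen is therefore aliased with village, and the plain regimen contrast at a given year is not estimable. The slope difference is estimable, and so is a contrast that averages each regimen's four village effects. Neither has any between-village error.

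**If village is left out altogether.** The design effect for a single-year contrast is 1 + (400 − 1) × ICC, and the naive type I error is 2Φ(−1.96/√DEFF).

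- ICC 0.002: DEFF = 1 + 399 × 0.002 = 1.80, error 14%.
- ICC 0.01: DEFF = 1 + 399 × 0.01 = 4.99, error 38%.

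Both ICCs are assumptions.

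**Size for the slope test.** Null simulation, 2,000 replicates per setting.

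- From the documents: 4 v 4 villages, about 100 households and 400 people per village, two-sided 5%. Section 5 asks for a baseline MF rate of at least 10%.
- Assumed: baseline prevalence about 10%, 18% or 30%; decline 0.45 logit per year; household SD 0.8; village intercept SD 0.4; four or five surveys; between-village slope SD from 0 to 0.15 logit per year.
- Model: logistic with eight village effects, year and regimen by year. A household-clustered sandwich SE stands in for the household-level GLMM.

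Rejection rates (range over baselines):

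| Slope test | SD 0 | SD 0.05 | SD 0.10 | SD 0.15 |
|---|---|---|---|---|
| Household-level robust, 5 surveys | 5–6% | 9–16% | 22–36% | 37–53% |
| Household-level robust, 4 surveys | 5–6% | 9–10% | 15–25% | 28–39% |
| Village-level robust, uncorrected, normal reference | 13–18% | 13–18% | 13–18% | 13–18% |
| t-test on 8 village slopes (6 df, critical value 2.447) | 4–6% | 4–6% | 4–6% | 4–6% |

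Different assumptions give the same pattern. With baseline 20%, yearly odds ratio 0.6, household SD 0.7, village intercept SD 0.3, and village slopes and village-year deviations sharing the same SD, the household-level test rejects in 11.5–14.6% at SD 0.05, 26–34% at 0.1 and 53–61% at 0.2. The t-test on village slopes gives 4.3–6.4%.

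**Yearly contrasts.** The averaged regimen contrast at the last survey, with village intercept SD 0.4, rejects in 30–48% of null trials even at slope SD 0. Change from baseline, tested on 6 df, gives 4–5%.

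**Price of a correct error term.** The detectable slope difference at 80% power on 6 df is 3.37 × (SD of estimated village slopes) × √(1/4 + 1/4). At true slope SD 0.10–0.15 the SD of estimated slopes is about 0.108–0.187.

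- 3.37 × 0.108 × 0.707 = 0.26 logit per year.
- 3.37 × 0.187 × 0.707 = 0.45 logit per year.

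The assumed decline is itself 0.45 logit per year.

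**The case against.** The strongest reply is that section 7.4 is under-specified and not wrong. Its opening paragraph is general and speaks of a trend within each village, and the GLMM is offered only as an illustration, so random village slopes may be intended. The reference to households from the same site could mean nested random effects, and the robust variance could be clustered on village. The fixed-effect reading also makes the plan's own yearly contrasts inestimable, which is a reason to doubt it.

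This is fair up to a point: the text does not say fixed, and a random-slope reading of the opening paragraph is possible. But that paragraph uses the slopes for time-to-target estimates and never makes their spread the yardstick for the regimen test. The worked example lists its effects without a village-by-year term. A random village intercept alone would still leave the slope test without variation in slope.

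Clustering the robust variance on eight villages does not rescue it either. Much of the 13–18% does come from the normal reference, which the plan does not specify. With a 6-df t reference the uncorrected sandwich still rejected in about 7–11%.

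Three further points stand.

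- The documents give no village variance, so every error rate is illustrative.
- The household-clustered marginal model is a stand-in for the planned GLMM.
- The price assumes separate analyses per area. The plan does not say whether areas are pooled; with 8 v 8 villages the detectable difference would be about 0.16–0.29 logit per year.

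**Conclusion.** The concern holds and should be fixed before analysis. As naturally read, the primary test of twice-yearly against annual MDA has no between-village error term, and the two descriptions in section 7.4 are not reconciled. If villages decline at identical rates, the slope test keeps its 5% level. If they differ by an SD of 0.05 to 0.15 logit per year, false-positive rates of about 9% to 53% follow under the stated assumptions, depending on baseline prevalence and number of surveys. Nothing in the documents supports assuming that the difference is zero. The conclusion that the error term is missing rests on the layout and the wording; only the size depends on the assumed variances.

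**What to change.** In section 7.4:

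1. Reconcile the opening paragraph with the worked example, so that one model serves both the time-to-target estimates and the regimen test.
2. Replace sentinel site as a covariate by a random village intercept and a random village slope on year, nested in regimen, with household nested in village. Test regimen by year on about 6 df per study area. Alternatively, compare the 4 v 4 village slopes directly by t-test. The t-test is the option whose error rate was checked above. The random-slope GLMM was not simulated, and four villages per regimen say little about a slope variance.
3. State the cluster level of the robust variance, and do not use it uncorrected with eight clusters.
4. Define each yearly regimen contrast as a change from baseline, with the same between-village error.
5. State the limit that remains. If each regimen occupies a single zone per area, zone is confounded with regimen and no village term removes that; the report should say so.

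The plain chi-square test for treatment coverage should also allow for village and household clustering. This is a lesser point.

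The cost is SAP wording and a few lines of GLIMMIX code, with no new data. The real downside is wider intervals and the limited power shown above, which the design imposes.
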